9.3.7 Events of Clinical Interest (ECI)

Selected non-serious and serious adverse events are also known as Events of Clinical Interest (ECI) and must be reported to the Sponsor.

Events of clinical interest for this trial include:

- 1. an overdose of Sponsor's product, as defined in Section 9.4 Treatment of Overdose, that is not associated with clinical symptoms or abnormal laboratory results.
- 2. an elevated AST or ALT lab value that is greater than or equal to 3X the upper limit of normal and an elevated total bilirubin lab value that is greater than or equal to 2X the upper limit of normal and, at the same time, an alkaline phosphatase lab value that is less than 2X the upper limit of normal, as determined by way of protocol-specified laboratory testing or unscheduled laboratory testing.*

*Note: These criteria are based upon available regulatory guidance documents. The purpose of the criteria is to specify a threshold of abnormal hepatic tests that may require an additional evaluation for an underlying etiology. The trial site guidance for assessment and follow up of these criteria can be found in the Investigator Trial File Binder (or equivalent).

9.4 Treatment of Overdose

For purposes of this trial, an overdose will be defined as any dose exceeding the prescribed dose for MK-1308 or MK-1308A by \geq 150% (eg, \geq 1.5 times the indicated dose) based on the known dose-related toxicities of ipilimumab and for pembrolizumab \geq 1000 mg. No specific information is available on the treatment of overdose of MK-1308, MK-1308A, or pembrolizumab. In the event of overdose, MK-1308, MK-1308A, or pembrolizumab should be discontinued and the participant should be observed closely for signs of toxicity. Appropriate supportive treatment should be provided if clinically indicated.

9.5 Safety

Details regarding specific laboratory procedures/assessments to be performed in this trial are provided below. The total amount of blood/tissue to be drawn/collected over the course of the trial (from pre-trial to post-trial visits) can be found in Section 9.

Planned time points for all safety assessments are provided in the SoA.

9.5.1 Physical Examinations

The investigator or qualified designee will perform a complete physical exam including neurologic assessment during the screening period. Clinically significant abnormal findings should be recorded as medical history. The time points for full physical exam and directed physical examination are described in Section 2 – Schedule of Activities (SoA). After the first dose of trial treatment new clinically significant abnormal findings should be recorded as AEs.

9.5.2 Vital Signs

The investigator or qualified designee will obtain vital signs at screening, prior to the dosing of each treatment (MK-1308, MK-3475, or combo admixture), and at the end of infusion. Vital signs should also be collected at the End of Treatment Visit and Safety Follow-up (30-day and 90-day) Visits. Vital signs include temperature, pulse, respiratory rate, and blood pressure. Weight will be measured on Day 1 of each cycle (can be done at any time on Day 1 of each cycle). Height will be measured at the Screening visit only.

9.5.3 Electrocardiograms

Standard 12-lead ECGs will be performed using local standard procedures. The timing of ECGs is specified in the SoA in Section 2. Clinically significant abnormal findings at Screening should be recorded as medical history. Additional ECGs should be performed when clinically necessary.

9.5.4 Clinical Safety Laboratory Assessments

Refer to Appendix 2 for the list of clinical laboratory tests to be performed and to the SoA for the timing and frequency.

- The investigator must review the laboratory report, document this review, and record any clinically relevant changes occurring during the study in the AE section of the CRF. The laboratory reports must be filed with the source documents. Clinically significant abnormal laboratory findings are those which are not associated with the underlying disease, unless judged by the investigator to be more severe than expected for the participant's condition.
- All protocol-required laboratory assessments, as defined in Appendix 2, must be conducted in accordance with the laboratory manual and the SoA.
- If laboratory values from non-protocol specified laboratory assessments performed at the institution's local laboratory require a change in study participant management or are considered clinically significant by the investigator (eg, SAE or AE or dose modification), then the results must be recorded in the appropriate CRF (eg, SLAB).
- For any laboratory tests with values considered clinically significantly abnormal during participation in the study or within 30 days after the last dose of study treatment, every attempt should be made to perform repeat assessments until the values return to normal or baseline or if a new baseline is established as determined by the investigator.

For dose escalation and dose confirmation only, laboratory safety tests (hematology and chemistries) for screening period should be performed within 14 days prior to the first dose of trial treatment.

For efficacy expansion and coformulation phases, laboratory safety tests (hematology and chemistries only) should be performed and reviewed by the investigator or staff designee for eligibility within 72 hours prior to the first dose of trial treatment. All other required screening laboratory tests (including hepatitis, ACTH, cortisol, and thyroid function testing) may be performed anytime within 28 days prior to first dose. If the participant has had prior anti-PD-1 or PD-L1 treatment, the ACTH, cortisol and thyroid test results must be reviewed prior to C1D1 dosing. Laboratory safety tests conducted within 72 hours of C1D1 do not need to be repeated prior to C1D1 dosing.

Laboratory test results must be reviewed by the investigator or qualified designee and found to be acceptable prior to administration of each subsequent dose of trial treatment. However, in the event thyroid function test results after Cycle 1 are not available prior to scheduled dosing, review of thyroid function tests (T3, T4, and TSH), ACTH and cortisol results after dosing is acceptable. Unresolved abnormal laboratory values that are drug-related AEs should be followed until resolution. Laboratory tests do not need to be repeated after the end of treatment if laboratory results are within the normal range.

9.5.5 Pregnancy Testing

Pregnancy testing:

- Pregnancy testing requirements for study inclusion are described in Section 6.1.
- Pregnancy testing (urine or serum as required by local regulations) should be conducted at every cycle (Q6W), prior to dosing, during intervention.
- Pregnancy testing (urine or serum as required by local regulations) should be conducted at the end of relevant systemic exposure.
- Additional serum or urine pregnancy tests may be performed, as determined necessary by the investigator or required by local regulation, to establish the absence of pregnancy at any time during the subject's participation in the study.

9.6 Pharmacokinetics

Sample collections are planned for PK and ADA analysis for MK-1308 and pembrolizumab according to the SoA described in Section 2. Blood samples will be obtained to measure the PK of serum MK-1308 given as monotherapy and in combination with and in coformulation with pembrolizumab. If feasible, PK data of MK-1308 monotherapy and in combination and coformulation with pembrolizumab will be analyzed using nonlinear mixed effects modeling. A population PK analysis of MK-1308 may be performed to characterize PK parameters (ie, clearance, volume of distribution [V]) and evaluate the effect of extrinsic and intrinsic factors to support the proposed dosing regimen.

Pharmacokinetic data may also be used to explore the exposure-response relationships for MK-1308 anti-tumor activity/efficacy in combination with pembrolizumab, as well as safety in the proposed participant population. The results of these analyses, if performed, will be reported separately.

PK and ADA samples may be disposed of in accordance with sample destruction procedures once the PK and ADA data are finalized.

9.6.1 Blood Collection for Serum MK-1308

Sample collection, storage and shipment instructions for serum samples will be provided in the Procedures Manual.

Pharmacokinetic samples should be drawn according to the PK collection schedule for all participants. Every effort should be taken to collect samples at 30 days after end of study intervention.

9.6.2 Blood Collection for Serum Pembrolizumab

Sample collection, storage, and shipment instructions for serum samples will be provided in the Procedures Manual.

Pharmacokinetic samples should be drawn according to the PK collection schedule for participants who receive pembrolizumab. Every effort should be taken to collect samples at 30 days after end of study intervention.

9.6.3 Blood Collection for Anti-Pembrolizumab Antibodies

Sample collection, storage and shipment instructions for serum samples will be provided in the Procedures Manual. Anti-pembrolizumab antibody samples should be drawn according to the ADA collection schedule for participants who receive pembrolizumab. Simultaneous PK sampling is required for interpretation of ADA analysis. Every effort should be taken to collect samples at 30 days after end of study intervention for ADA. Simultaneous PK sampling is required for interpretation of ADA analysis.

9.6.4 Blood Collection for Anti-MK-1308 Antibodies

Sample collection, storage and shipment instructions for serum samples will be provided in the Procedures Manual. Anti-MK-1308 antibody samples should be drawn according to the ADA collection schedule for participants who receive MK-1308. Simultaneous PK sampling is required for interpretation of ADA analysis. Every effort should be taken to collect samples at 30 days after end of study intervention for ADA. Simultaneous PK sampling is required for interpretation of ADA analysis.

9.7 Pharmacodynamics

A direct receptor occupancy assay to measure target engagement cannot be used as CTLA4 expression on the cell surface of T-cells is transient and tightly regulated. Therefore, post-treatment changes in ALC and expression of T-cell activation markers (for example Ki67, ICOS, and HLA-DR) will be assessed in peripheral blood based on the proposed effect of CTLA4 blockade in the immune priming phase to increase activation and proliferation of T-cells.

Sample collection, storage and shipment instructions for blood samples will be provided in the Procedures Manual.

9.8 Future Biomedical Research Sample Collection

The following specimens are to be obtained as part of Future Biomedical Research (Not applicable for Arm K):

- Leftover main study tumor
- Leftover cells from mononuclear cells biomarker analysis
- Leftover serum from serum cytokine
- Leftover DNA from genetic analysis and T-cell repertoire
- Leftover RNA
- Leftover plasma from ctDNA
- Leftover and/or derivative from stool for biomarker analysis (Dose Escalation and Confirmation phases only)

9.9 Biomarkers

(This is not applicable to Arm K in China.)

Collection of samples for other biomarker research is also part of this study. The following samples for biomarker research are required and will be collected from all participants in this study as specified in the SoA. Sample collection, storage and shipment instructions for these samples will be provided in the Procedures Manual:

- Serum for cytokine measurements
- Blood for TCR repertoire
- Blood for RNA analyses
- Peripheral blood for immunophenotyping biomarker analyses
- Peripheral blood for mononuclear cells biomarker analysis
- Whole blood for exploratory T-cell response
- Blood for genetic analysis and HLA genotyping
- Tumor tissue
- Blood for ctDNA
- Stool microbiome collection (dose escalation, confirmation, and expansion phases only)

Pre- and on-treatment tumor tissue will be collected for additional biomarker analysis from approximately 10 participants each in Arms F and G. For these participants, an archival tumor sample is also requested, if feasible, from a time point before receiving any prior immune-oncology treatment. New biopsies of tumor tissue will be obtained from these participants at Screening (following confirmation of all other eligibility assessments) and at 4 weeks after C1D1 (\pm 7 days). Tumor tissue from Screening should be accurately marked so

the same lesion site can be used for the on-treatment biopsy. If not possible, the Sponsor should be notified of the location.

9.9.1 Planned Genetic Analysis Sample Collection

This sample should be drawn for HLA genotyping and for planned analysis of the association between genetic variants in DNA and drug response. Data analysis will be limited to HLA if there is either a local law or regulation prohibiting collection, or if the IRB/IEC does not approve the collection of the sample for these purposes. If the sample is collected, leftover extracted DNA will be stored for future biomedical research if the participant signs the FBR consent. If the planned genetic analysis is not approved, but FBR is approved and consent is given, this sample will be collected for the purpose of FBR.

9.10 Visit Requirements

Visit requirements are outlined in Section 2 – Schedule of Activities (SoA). Specific procedure-related details are provided above in Section 9 – Study Assessments and Procedures.

9.10.1 Screening

Approximately 28 days prior to treatment allocation/randomization, potential participants will be evaluated to determine that they fulfill the entry requirements as set forth in Section 5.1. Screening procedures may be repeated after consultation with the Sponsor.

Documented informed consent must be obtained prior to performing any protocol-specific procedure. Results of a test performed prior to the participant signing consent as part of routine management are acceptable in lieu of a screening test if performed within the specified time frame. Screening procedures are to be completed within 28 days prior to the first dose of trial treatment except for the following:

- For dose escalation and dose confirmation, safety laboratory tests are to be performed within 14 days prior to the first dose of trial treatment. If these tests are performed within 72 hours of C1D1, they do not need to be collected earlier in screening.
- For efficacy expansion and coformulation phases, laboratory safety tests (hematology and chemistries) should be performed and reviewed by the investigator or staff designee for eligibility within 72 hours prior to the first dose of trial treatment. All other required laboratory tests can be performed anytime within the 28-day screening period.
- Evaluation of ECOG must be performed within 3 days (72 hours) prior to the first dose of trial treatment.
- For women of reproductive potential, a urine or serum pregnancy test will be performed within 24 hours for urine and within 72 hours for serum prior to the first dose of trial treatment and prior to each subsequent dose. If urine pregnancy results cannot be confirmed as negative, a serum pregnancy test will be required (performed by the local study site laboratory).
- Archival or newly obtained tumor sample collection is required to be submitted within 28 days prior to the first dose of trial treatment.

• Participants may be re-screened up to 2 times with consultation and approval of the Sponsor.

9.10.2 Treatment Period

Visit requirements are outlined in Section 2.0 – Schedule of Activities (SoA). Specific procedure-related details are provided above in Section 9.1 – Administrative and General Procedures.

9.10.3 Discontinued Participants Continuing to be Monitored in the Study

The mandatory Safety Follow-up Visit should be conducted approximately 30 days after the last dose of trial treatment or before the initiation of a new anticancer treatment, whichever comes first. For the efficacy expansion and coformulation phases, a second mandatory Safety Follow-up Visit should be conducted approximately 90 days after the last dose of trial treatment or before the initiation of a new anticancer treatment, whichever comes first.

All AEs that occur prior to the Safety Follow-up visits should be recorded (up to 90 days following end of treatment). Participants with an AE of Grade > 1 will be followed until the resolution of the AE to Grade 0-1 or until the beginning of a new anticancer therapy, whichever occurs first. All AEs from the time of treatment allocation/randomization through 90 days following cessation of study treatment must be reported by the investigator. All AEs meeting serious criteria, from the time of treatment allocation/randomization through 90 days following cessation of study treatment, or 30 days following cessation of study treatment if the participant initiates new anticancer therapy, whichever is earlier must be reported by the investigator.

9.10.4 Post-Study

Participants will be required to return to clinic approximately 30 days after the last dose of study treatment for the post-trial visit. If the post-trial visit occurs less than 30 days after the last dose of study treatment, a subsequent follow-up phone call should be made at 30 days post the last dose of study treatment to determine if any AEs have occurred since the post-trial clinic visit.

For the efficacy expansion and coformulation phases, participants also will be required to return to clinic approximately 90 days after the last dose of study treatment for a post-trial visit. If the post-trial visit occurs less than 90 days after the last dose of study treatment, a subsequent follow-up phone call should be made at 90 days post the last dose of study treatment to determine if any AEs have occurred since the 30-day post-trial clinic visit.

9.10.5 Survival Follow-up

Participants who experience confirmed disease progression or start a new anticancer therapy, will move into the Survival Follow-Up Phase and should be contacted by telephone every 12 weeks to assess for survival status until death, withdrawal of consent, or the end of the trial, whichever occurs first.

9.10.6 Survival Status

To ensure current and complete survival data is available at the time of database locks, updated survival status may be requested during the course of the study by the Sponsor. For example, updated survival status may be requested prior to but not limited to an eDMC review, interim and/or final analysis. Upon Sponsor notification, all participants who do not/will not have a scheduled study visit or study contact during the Sponsor-defined time period will be contacted for their survival status (excluding participants who have previously recorded a death event in the collection tool).

10. Statistical Analysis Plan

This section outlines the statistical analysis strategies and procedures for the primary and secondary analyses of the study. Exploratory and other non-confirmatory analyses will be outlined in a separate supplemental Statistical Analysis Plan (sSAP).

If, after the study has begun, changes are made to primary and/or secondary objectives, or the statistical methods related to those objectives, then the protocol will be amended (consistent with ICH Guideline E9). Changes to exploratory or other non-confirmatory analyses made after the protocol has been finalized, but prior to the conduct of any analyses, will be documented in the sSAP as needed and referenced in the Clinical Study Report (CSR) for the study.

10.1 Statistical Analysis Plan Summary

This section contains a brief summary of the statistical analyses for this trial. Full details are in the Statistical Analysis Plan, Section 10.2 through Section 10.12.

Study Design Overview	Phase 1 / 2 trial of MK-1308 in combination with pembrolizumab in participants with advanced/metastatic solid tumors.	
Analysis Populations	Safety (Primary): All-Participants-as-Treated (APaT), DLT-evaluable population for DLT analysis	
	PK (Secondary): Per-Protocol (PP)	
	Efficacy (Primary in the efficacy expansion phase, and secondary for the other phases): APaT population	

Primary Endpoint(s)	 Safety: Number of participants with at least 1 DLT Number of participants with ≥1 AE Number of participants discontinuing study treatment due to an AE Efficacy (efficacy expansion phase): Objective Response Rate (ORR) defined as the portion of participants with CR or PR as assessed by BICR based on RECIST 1.1, adjusted to follow a maximum of 10 target lesions and a maximum of 5 target lesions per organ)
Secondary Endpoints	ORR as assessed by the investigator based on RECIST 1.1 (dose escalation phase, dose confirmation phase, and Arm I and K in the coformulation phase): DOR as assessed by BICR based on RECIST 1.1 (efficacy expansion phase):
	 The time from first documented evidence of CR or PR until disease progression or death due to any cause, whichever occurs first (for responders only) PK profile and ADA of MK-1308 monotherapy and MK- 1308 in combination with pembrolizumab; PK parameters
	of pembrolizumab in combination with pembrolizumab, FK parameters of pembrolizumab in combination with MK-1308; PK profiles of MK-1308 and pembrolizumab when drugs are sequentially administered, co-administered and coformulated as MK-1308A. • AUC, C _{min} , C _{max}
	Anti-drug antibody levels
Statistical Methods for Efficacy/Immunogenicity/	ORR will be summarized by treatment arm along with a 95% confidence interval.
Pharmacokinetic Analyses	Descriptive summary statistics will be provided for DOR. Time-to-event analysis and Kaplan-Meier estimates may be provided for DOR in addition to the descriptive summary statistics if there are at least 10 responders. PK parameters of study medicines will be summarized by planned visit and time for each dose cohort.

Treatment Assignment	Participants will be allocated to receive MK-1308 in combination with pembrolizumab (Arms A-F), or MK-1308 monotherapy (Arm G), or the coformulation product MK-1308A (Arm I and K) using an IVRS/IWRS. Treatment assignments in the dose escalation phase, dose confirmation phase and coformulation phase are non- random. Treatment assignments in the efficacy expansion phase will utilize random assignment whenever there is more than 1 treatment arm open.
Statistical Methods for Safety Analyses	Summary statistics will be provided for the safety endpoints as appropriate.
Sample Size and Power	The sample size in Cohorts 1, 2, 3 and Arms A, B, C, D, E of this study depends on the observed DLT profiles of MK-1308 in combination with pembrolizumab. Maximum sample size will be 100 in Arm F and 40 in Arm G. Target sample size will be 20 in Arm I, and 20 in Arm K. A target sample size of 348 participants will be used for study planning purposes.

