A safety interim analysis will be conducted when the first 6 DLT-evaluable participants have completed their DLT evaluation. Up to 8 participants may be enrolled initially to achieve the desired sample size of 6 DLT-evaluable participants. If the observed DLT rate is higher than 25%, the 400 mg O6W pembrolizumab dosing may be replaced with pembrolizumab 200 mg Q3W in the newly enrolled participants (Arm H; not activated). The decision to switch from pembrolizumab 400 mg Q6W to 200 mg Q3W will be based on the totality of the safety data and not limited to DLTs. If needed, up to 14 participants will be evaluated for DLT and additional safety interim analyses will be conducted after the first safety interim analysis of 6 DLT-evaluable participants and before the final decision of the dose and frequency of the combination is determined. If the decision to switch from pembrolizumab 400 mg Q6W to 200 mg Q3W is made, existing participants who have already been treated with pembrolizumab 400 mg Q6W plus MK-1308 25 mg Q6W may also be switched to pembrolizumab 200 mg Q3W plus MK-1308 25 mg Q6W, after discussion with the Sponsor. As soon as the DLT and safety evaluation is complete and the dose and frequency are decided, randomization between Arm F and Arm G (described below) will begin. A total of 100 new participants in the pembrolizumab 200 Q3W plus MK-1308 25 mg Q6W will be planned for enrollment, taking into consideration the efficacy interim analysis, if an alternate dosing regimen is chosen.

Note: The DLT period with the first 6 subjects concluded with no toxicity concerns. Arm H is not required and will not be activated.

Regardless of the dosing regimen chosen, an efficacy interim analysis will be conducted approximately 9 weeks after the first dose of the 20th participant. If at least 4 out of the first 20 participants (ie, at least 20%) experience a response, Arm F will continue to enroll a maximum of 80 additional participants for a total of 100 participants at the same dose level. Enrollment to Arm F may not be paused to wait for results of the efficacy interim analysis. If fewer than 20% responses are observed, the totality of the data will be evaluated to decide whether or not to continue enrollment in Arm F.

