9.2.1.4 Tumor Imaging During the Study

The first on-trial imaging assessment should be performed at 9 weeks (\pm 7 days) from the date of first dose of study drug. Subsequent tumor imaging should be performed every 9 weeks (63 days \pm 7 days) or more frequently if clinically indicated. After 54 weeks, participants who remain on-treatment will have imaging performed every 12 weeks (84 days \pm 7 days), or sooner if clinically indicated, for all cohorts. Imaging timing should follow calendar days from treatment initiation and should not be adjusted for delays in cycle starts. Imaging should continue to be performed until disease progression is identified by the investigator, unless the investigator elects to continue treatment and follow irRECIST in the dose escalation phase and the dose confirmation phase (see Section 9.2.1.8) or iRECIST in the efficacy expansion and coformulation phases (see Section 9.2.1.9), the start of new anticancer treatment, withdrawal of consent, death, or notification by the Sponsor, whichever occurs first. All supplemental imaging must be submitted to the CIV.

Per RECIST 1.1 (Section 9.2.1.7), PR and CR should be confirmed by a repeat imaging assessment. The tumor imaging for confirmation of response may be performed \geq 4 weeks after the first indication of response or at the next scheduled scan (ie, 9 weeks later), whichever is clinically indicated. Participants will then return to regular scheduled imaging every 9 weeks, starting with the next scheduled imaging time point. Participants who receive additional imaging for confirmation do not need to undergo the next scheduled tumor imaging if it is less than 4 weeks later; tumor imaging may resume at the subsequent scheduled imaging time point.

On-study brain imaging should be performed if clinically indicated or to confirm CR (if other lesions indicate CR and brain lesions existed at Screening).

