Per iRECIST (Section 9.2.1.9), disease progression should be confirmed by the site 4 to 8 weeks after site-assessed first radiologic evidence of progressive disease in clinically stable participants. Participants who have unconfirmed disease progression may continue on treatment at the discretion of the site investigator until progression is confirmed by the site. Participants who obtain a confirmation scan do not need to undergo the next scheduled tumor imaging if it is <4 weeks later; tumor imaging may resume at the subsequent scheduled imaging time point if clinically stable. Participants who have confirmed disease progression as assessed by the site will discontinue the treatment. Exceptions are detailed in Section 9.2.1.9.

For participants in Arm G, in order to be eligible to crossover, site-assessed radiographic PD must be verified by BICR. When the investigator identifies radiographic progression per RECIST 1.1 for participants in Arm G, the imaging should be submitted to CIV. Tumor imaging should be used as a new baseline for the participant for VOP by BICR. The CIV will perform expedited review and communicate the VOP results to the study site and Sponsor via email. In clinically stable participants, imaging should continue until PD has been verified by BICR (if initial site-assessed PD was not verified by BICR, each subsequent scan must be submitted to CIV with verification of PD request until PD has been verified by BICR).

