9.2.1.5 End of Treatment and Follow-up Tumor Imaging

For participants who discontinue trial treatment, tumor imaging should be performed at the time of treatment discontinuation (\pm 4 week window). If a previous scan was obtained within 4 weeks prior to the date of discontinuation, then a scan at treatment discontinuation is not mandatory. For participants who discontinue trial treatment due to documented disease progression, this is the final required tumor imaging if the investigator elects not to implement irRECIST or iRECIST.

For participants who discontinue study treatment without documented disease progression, every effort should be made to continue monitoring disease status by tumor imaging using the same imaging schedule used while on treatment calculated from the date of first dose (see Section 9.2.1.4) until the start of a new anticancer treatment, disease progression, pregnancy, death, withdrawal of consent, or the end of the study, whichever occurs first.

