10.6.1 Statistical Methods for Efficacy Analysis

Objective response rate will be summarized by arm along with a 95% confidence interval. Confidence interval would be calculated using the Clopper–Pearson method. The Miettinen and Nurminen method [Miettinen, O. 1985] will be used for comparison of the ORR between Arm F and Arm G.

Duration of Response will be summarized either using descriptive summary statistics or Kaplan-Meier estimates, depending on the number of responders.

Time to response and best overall response will also be summarized.

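### Do the two duration-of-response sentences in Sections 10.1 and 10.6.1 leave the Arm F and G analysis undefined?

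*Combined protocol and SAP*

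**What the plan says.** Section 10.1, the summary table, commits to descriptive statistics for DOR and then says "Time-to-event analysis and Kaplan-Meier estimates may be provided for DOR in addition to the descriptive summary statistics if there are at least 10 responders". Section 10.6.1, the methods text, says "Duration of Response will be summarized either using descriptive summary statistics or Kaplan-Meier estimates, depending on the number of responders". Just before that, on response rate, it says "Objective response rate will be summarized by arm along with a 95% confidence interval".

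Section 10.4.1 gives the start of DOR (first evidence of response) and its event (progression or death), without a censoring rule. Section 10 opens with "This section outlines the statistical analysis strategies and procedures for the primary and secondary analyses of the study", so DOR, a secondary endpoint, belongs there.

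Three imaging rules affect how long a responder is followed:

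- Section 9.2.1.4, on-study imaging: "Imaging should continue to be performed until disease progression is identified by the investigator, unless the investigator elects to continue treatment" under irRECIST or iRECIST.
- Section 9.2.1.4, Arm G, for the crossover decision: "In clinically stable participants, imaging should continue until PD has been verified by BICR".
- Section 9.2.1.5, after stopping treatment without progression, imaging runs "until the start of a new anticancer treatment, disease progression, pregnancy, death, withdrawal of consent, or the end of the study, whichever occurs first".

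**The concern.** On a literal reading the two sections disagree. One makes Kaplan-Meier an optional extra on top of a descriptive summary; the other makes it one of two alternatives. The section that should carry the detail drops the threshold that the summary states, and neither sentence says whether 10 is counted per arm or over both arms.

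The missing censoring rule looks more serious. Some responses will be ongoing at cutoff, and some imaging will end early by design. DOR is judged by BICR, yet imaging can end when the investigator calls progression. Only Arm G has a written instruction to keep scanning until BICR agrees. If descriptive statistics meant the plain median of observed durations, ongoing responses would be counted as finished and DOR understated. Arms F and G could also be followed to different depths for the same endpoint.

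**Working it through.** The plan states no DOR figure to reproduce. The check is a comparison of the texts plus two calculations.

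**1. Can the sections be read together?**

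| | Section 10.1 | Section 10.6.1 |
|---|---|---|
| Kaplan-Meier depends on | number of responders | number of responders |
| Threshold | 10 | not given |
| Force | optional | one of two methods will be used |
| Relation to descriptive summary | additional | alternative |

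They agree on what triggers Kaplan-Meier. Section 10.6.1 leaves out the number but does not give a different one. Put the 10 from Section 10.1 into Section 10.6.1 and the rule is Kaplan-Meier at 10 or more responders and a descriptive summary below that. Showing both at 10 or more satisfies Section 10.1 as well. Since response rate is summarised by arm in the same paragraph, per arm is the natural count.

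**2. Which arm does the threshold affect?**

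Inputs: maximum 100 in Arm F and 40 in Arm G (Section 10.9). True response rates are assumed; 20% matches the Arm F interim benchmark in Section 5.1.3 ("If at least 4 out of the first 20 participants (ie, at least 20%) experience a response"), that is 4/20. With X ~ Binomial(n, p), Pr(X ≥ 10) = 1 − Pr(X ≤ 9):

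| Assumed rate | Arm F, n = 100 | Arm G, n = 40 |
|---|---|---|
| 10% | 54.9% | 0.5% |
| 15% | 94.5% | 6.7% |
| 20% | 99.8% | 26.8% |
| 25% | above 99.9% | 56.1% |
| 30% | above 99.9% | 80.4% |

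At 20%, Arm F expects 0.20 × 100 = 20 responders and would almost surely get Kaplan-Meier. Arm G's interim rule needs only 1/20 = 5%, which is 0.05 × 40 = 2 responders at full size. With so few, a listing is as informative as a curve.

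**3. How bad is the worst reading?**

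Assumptions, none from the documents: exponential DOR, follow-up after response uniform over the stated window, and a raw median that treats ongoing responses as ended. Medians in months over simulated trials:

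| True median | Follow-up | Responders | Raw | Kaplan-Meier |
|---|---|---|---|---|
| 12 | 6–18 | 20 | 8.3 | 12.0 |
| 24 | 12–36 | 20 | 16.6 | 23.9 |
| 12 | 12–36 | 20 | 11.8 | 11.2 |
| 12 | 6–18 | 4 | 8.4 | 8.6 |
| 24 | 12–36 | 4 | 16.8 | 17.3 |
| 12 | 12–36 | 4 | 11.7 | 8.4 |

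Here the Kaplan-Meier median is the first time the curve reaches 0.5 or less, which runs low at even counts. Taking the midpoint where the curve sits exactly at 0.5 moves the third row to about 12.0 and the last to about 11.2. The first two rows barely move. So the raw reading does real harm when about half the responses (51%) are ongoing, and little when follow-up is mature (27% ongoing).

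**4. Do the imaging rules leave a gap between the arms?**

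- Section 9.2.1.9 keeps clinically stable participants in the expansion phase on treatment until the investigator confirms progression, with repeat imaging at 4 to 8 weeks. Stable Arm F participants therefore normally have scans after the first investigator call too.
- Section 9.2.1 sends all scans, scheduled or not, to the central imaging vendor.
- Crossover from Arm G requires BICR-verified progression (Sections 5.1.3 and 9.2.1.6), so the DOR event has already occurred by then.
- Section 10.6.1 compares the arms on response rate only. No DOR comparison is visible.

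What is left is a narrow group: clinically unstable participants, or those whose investigator-confirmed progression BICR does not find.

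**The case for a change.** The best case for a change is that the trial is open-label, the DOR wording is loose, and Section 10 says that changes to methods for secondary objectives go through an amendment. Settling the wording before analysis would remove any suspicion that the method was picked after seeing the data. Section 10.6 claims to cover secondary objectives, its DOR sentence is fully visible, and it contains no censoring rule. Read alone, the word may in Section 10.1 would permit a report with no Kaplan-Meier estimate even with 20 responders.

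Part of this stands. The sections do differ on whether Kaplan-Meier is optional and whether it replaces or supplements the descriptive summary. The residual imaging gap is also real, and no figure in the documents sizes it.

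The rest does not carry. Reading Section 10.1 alone ignores Section 10.6.1, where the method is set by the responder count. The missing rule cannot be shown to be missing: the contents list blacks out everything between Sections 10.6.3.2 and 10.9, and Tables 9 to 12. The large differences in medians depend on a raw-median practice that no visible passage describes.

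**Conclusion.** No change is needed. The wording mismatch is a drafting slip that resolves when the two sections are read together, and the visible censoring gap is one that trial statisticians fill in a standard way: responders without an event are censored at their last adequate assessment, and small arms are shown as individual durations with ongoing responses marked. DOR here is a descriptive secondary endpoint, and no visible alpha, sample size, interim rule or between-arm test rests on it.

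The conclusion assumes that the threshold of 10 applies per arm and that analysts would not count ongoing responses as ended. If that second assumption failed, the Arm F median could be understated by roughly 30% with immature follow-up (8.3 against 12.0 months: 3.7/12.0 = 31%), and hardly at all with mature follow-up. Nothing visible in the plan points to that practice. The unquantified remainder, investigator progression that BICR does not confirm, affects a limited group and no stated comparison.
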